5.2 Endpoints

5.2.1 Primary Endpoint

The primary performance endpoint is the incidence of hernia recurrence within 3 months following the use of MaxTack[™] Motorized Fixation Device for fixation in minimally invasive ventral hernia repair procedures.

AFFIX (MaxTa Clinical Invest				
MDT23014	Revision	3.0	Page 22 of 97	Medtronic

Hernia recurrence is defined as a palpable fascial defect and/or a clinically manifested bulge, exacerbated by a Valsalva maneuver evaluated during a physical examination by the investigator and confirmed per site standard of care medical imaging, if necessary, at the respective clinical site. If a Valsalva maneuver is not conducted during physical examination, this must be reported as a protocol deviation.

If standard of care imaging (Computerized Tomography Scan (CT scan), ultrasound, or Magnetic Resonance Imaging (MRI)) is done for hernia recurrence confirmation at the discretion of the study investigator, the final decision to report a hernia recurrence will be based on the study investigator's assessment. Standard of care imaging may be done by a non-study, standard of care assessor, such as a radiologist.

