A Medical Monitor (MM) will be utilized to conduct an independent review and adjudication of specified adverse events. The assessments from the MM will be used in the study endpoint analyses where applicable.

The expected total study duration from the first subject enrollment to the last subject visit is approximately 25 months, representing approximately 13 months of enrollment and 12 months (+ 45 days) of subject follow-up. Assessments will occur at Screening, Operative, Discharge, Month 1, Month 3, and Month 12. The expected duration of each subject's participation in the study from Screening visit to the Month 12 is up to 15.5 months (screening visit could occur 60 days prior to the Operative day, and with the Month 12 follow-up having an upper window of 45 days). Study subjects will be followed until the final study visit or official study closure, defined as when Medtronic requirements have been satisfied per the CIP and/or by a decision by Medtronic, Institutional Review Board (IRB), or Ethics Committee (EC), or Regulatory Authority (RA), whichever occurs first.

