10.2 Data Collection

Subjects will be evaluated at screening, operative day, discharge, and postoperatively at Month 1, 3, and 12.

Table 3: Data Collection

		Visit (Days from Procedure)							
Assessment	Screening ¹ (-60-0 Days)	Operative Day	Discharge	Month 1 (30-51 Days)	Month 3 (90-120 Days)	Month 12 (365-410 Days)	Unscheduled Visit		
Informed Consent ¹	X1								
Subject Eligibility	X ²	X ²							
Medical Record Review and Physical Exam ⁴	х								
Medication Assessment ⁵	х	х	х	х	х	х	х		
HerQLes Quality of Life Questionnaire	х			х	х	х			
Pain (Numerical Rating Scale (NRS)) at Hernia Site	х			х	х	х			
Hernia Repair Procedure ⁶		X							
Surgeon Satisfaction Questionnaire		х							
Length of Hospital Stay			х						
Clinical Assessment ⁷				х	х	х	х		
Exit Subject						X ³			
Adverse Event Evaluation ⁸		X	Х	х	х	х	Х		
Device Deficiency Evaluation ⁸		х	Х	х	х	х	Х		
Protocol Deviation Evaluation	х	x	Х	х	х	х	Х		

1) Written Informed Consent must be obtained prior to any non-standard of care study assessments.

2) Screening may occur on the same day as Operative Day. If the Screening and Operative visits occur on different days, study eligibility assessments that occur at Screening must be reconfirmed on the Operative day.

3) Exit is to occur at the Month 12 visit unless the subject exits early (refer to Section 10.14.5 regarding details and procedures related to subjects considered Lost to Follow-up (LTFU)). 4) Medical Record Review and Physical Exam includes demography, medical history, surgical history, and weight/height

5) Medication Assessment includes prophylactic antibiotics, anticoagulants, antiplatelets, antithrombotic, and/or pain medication; where applicable

6) Hernia Repair Procedure includes operative times, general anesthesia information, hernia defect description, defect closure and surgical technique, tack, mesh and other fixation data 7) Clinical Assessment includes a Valsalva Maneuver during a physical examination for hernia recurrence, details of hernia recurrences / reoperation if applicable

8) See Section 12 for AE and DD reporting requirements

Medtronic Business Restricted

AFFIX (MaxTac Clinical Investi				
MDT23014	Revision	3.0	Page 38 of 97	Medtronic

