12.1 Adverse Events

The following AEs are required to be reported in the study after the point of skin incision until the subject exists:

- All AEs related to the MaxTack[™] Motorized Fixation Device, mesh, or study procedure
- All events that lead to death, regardless of relatedness
- Any non-subject adverse event

Reporting of these events to Medtronic will occur on the applicable AE eCRF. Each event must be reported separately. Documented pre-existing conditions are not considered AEs unless the nature or severity of the condition has worsened. Subject deaths are required to be reported. Refer to Section 12.7 for Subject Death collection and reporting requirements.

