12.4.1 Adverse Event and Device Deficiency Classification

All AEs and DDs will be reviewed by a Medtronic representative. AEs and DDs will be classified according to the definitions provided.

Upon receipt of an AE, a Medtronic representative will review the AE/DD for completeness and accuracy and when necessary, will request clarification and/or additional information from the Investigator. Medtronic will utilize Medical Dictionary for Regulatory Activities (MedDRA) for Regulatory Activities, to assign a MedDRA term for each AE based on the information provided by the investigator.

Regulatory reporting of AEs and DDs will be completed according to local regulatory requirements. Refer to Table 6 for a list of site reporting requirement timeframes. It is the responsibility of site and Medtronic to abide by any additional AE reporting requirements stipulated by the IRB/EC responsible for oversight of the study.

AFFIX (MaxTack [™] Motorized Fixation Device) Clinical Investigation Plan				
MDT23014	Revision	3.0	Page 55 of 97	Medtronic

Table 8: Adverse Event and Device Deficiency Classification Responsibilities

What is classified?	Who classifies?	Classification Parameters
Relatedness	Investigator	MaxTack [™] Device, mesh, study procedure
Relateuriess	Sponsor	MaxTack [™] Device, mesh, study procedure
Seriousness	Investigator	SAE, DD with SADE potential
Senousness	Sponsor	SAE, DD with SADE potential
Diagnosis	Investigator	Based on presenting signs and symptoms and other supporting data
Diagnosis	Sponsor	MedDRA term assigned based on the data provided by Investigator

Appendix I contains the Foreseeable Adverse Event List (FAL), which is a list of AEs related to the device or procedure that have been observed in previous studies and may be experienced by subjects.

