13.1 Independent Medical Monitor

At regular intervals, an independent Medical Monitor (MM) will conduct an independent adjudication of specified adverse events for subjects participating in the study. Source documents to support adjudication may be requested.

The MM will be a board-certified/board-eligible physician with expertise in hernia surgery and experience in the use of similar tacking devices. This physician will not be employed by Medtronic, will not be a participating investigator in the study, and will possess the necessary qualifications through education, training, and relevant experience to oversee the product's use and associated procedures.

Most adjudications will be conducted independently by the MM via entry of their assessments into the database. Medtronic personnel may facilitate adjudication meetings if needed, but the final adjudication decision will be solely from the MM.

If the MM disagrees with the investigator's classification of the event, the MM assessment will be provided to the investigator. If the investigator agrees with the MM's adjudication, the investigator is responsible for updating the AE CRF accordingly.

If the investigator does not agree with the MM's adjudication classification, both determinations will be provided within the final report; however, the MM's adjudication will be used for data analysis. If required, both determinations will be included in reporting to IRB/ECs and regulatory authorities.

14. Statistical Design and Methods

This section presents statistical considerations and justification for the study design and provides a highlevel description of planned analysis and reporting. More details will be given in a separate Statistical Analysis Plan (SAP) that will be finalized and approved before first data freeze or lock. Any deviation to the prespecified statistical analyses including justification, will be noted in the clinical study report(s).

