18.9 Appendix I – Foreseeable Adverse Events List

The information provided in this section pertains to foreseeable adverse events that may be observed in the AFFIX study and may collectively assist in identifying those events for a given device or therapy that are unexpected in nature.

An evaluation of potentially anticipated events, adverse device effects observed in previous clinical studies, and reported events in literature may be used in combination with device labeling, current event reporting information, and other published data to assess for an unexpected occurrence.

The MaxTack[™] Motorized Fixation Device involves surgery when used to fix prosthetic material to soft tissue in minimally invasive ventral hernia repair procedures. Therefore, standard adverse events associated with a surgical procedure may be experienced (e.g., anesthesia complications, infections, bleeding, etc.). However, the focus of this section is to address in more detail the foreseeable events due to the use, performance, and/or presence of the MaxTack[™] Motorized Fixation Device under investigation.

The procedure (ventral hernia repair) and the devices (mesh + tack) are closely interrelated, so it may be difficult to identify the origin of the complications (i.e., procedure-related versus device-related). The most common complications that may occur after a ventral hernia repair procedure, regardless of the type of mesh or tack used, include hernia recurrence, pain, and seroma. Treatment required for procedure and/or device-related adverse events may include medication, device surgical removal, or other surgical and medical remedies.

Potential risks associated with the implantation of the MaxTack[™] Motorized Fixation Device and risk minimization are discussed in Section 11. The risk management process for MaxTack[™] is performed in accordance with ISO 14971:2019 and ensures that the level of risk is acceptable prior to starting the study.

The foreseeable adverse events information presented in this section consists of three parts:

- 1) Observed adverse device effects in similar Medtronic studies,
- 2) Adverse events reported in published literature, and
- 3) Additional foreseeable adverse events.

Observed Adverse Device Effects (ADEs) in similar Medtronic Clinical Studies

MaxTack[™] just launched in the USA; at the moment of the CIP revision, there is no history of adverse events with this specific device and no indication that can be reported.

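### Does the protocol leave open whose judgement of hernia recurrence, the investigator's or the Medical Monitor's, decides the primary endpoint?

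*Protocol*

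**What the plan says.** Section 5.2.1 defines recurrence by physical examination with a Valsalva maneuver, confirmed by imaging where necessary. When imaging is used, "the final decision to report a hernia recurrence will be based on the study investigator", meaning that person's assessment. The next sentence allows the imaging to be done by someone outside the study, such as a radiologist.

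Section 13.1 says the Medical Monitor "will conduct an independent adjudication of specified adverse events for subjects participating in the study". If the investigator accepts a differing view from the Monitor, "the investigator is responsible for updating the AE CRF accordingly". If not, both determinations go into the final report and the Monitor's is analysed. Section 6 adds: "The assessments from the MM will be used in the study endpoint analyses where applicable". The adjudicated events are not listed.

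Recurrence appears in two places in the data flow. Footnote 7 to Table 3 (Section 10.2) puts "details of hernia recurrences / reoperation if applicable" in the Clinical Assessment. Section 12.4.1 describes Appendix I as one "which is a list of AEs related to the device or procedure that have been observed in previous studies", and Appendix I states that the most common complications of the repair "include hernia recurrence, pain, and seroma". For related adverse events, Section 12.1 says: "Reporting of these events to Medtronic will occur on the applicable AE eCRF".

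Section 14.4.4 tests the count with an exact binomial test on the full analysis set and does not name the form or the assessor that supplies recurrence status.

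**The concern.** The study is open-label and single-arm, and it has one hypothesis test, which rests on a handful of events. Sections 5.2.1 and 13.1 appear to give the last word to different people, and recurrence could plausibly come under both. If recurrence is also filed as an adverse event and the Monitor changes its diagnosis, Section 13.1 mentions an update to the adverse event form only, so the Clinical Assessment might still show the old status. One reclassified event at the boundary would turn a met goal into a missed one, or the reverse. A source chosen after the events are known would weaken the claim of a pre-specified test.

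A related worry is that Section 5.2.1 speaks of examination by the investigator, while Section 10.10 takes details from outside medical records when the subject sees a non-study physician. It may seem unclear whether such recurrences count.

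**Working it through.** **The plan's own figures.** Inputs: goal 8.6% and a two-sided 95% Clopper-Pearson interval (Sections 14.4.3 and 14.4.4); 100 evaluable subjects, assumed rate 1.0%, one-sided alpha 0.025, attrition 9% (Section 14.6).

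- Upper limit for x events in n = the 0.975 quantile of Beta(x + 1, n − x). For 3/100, Beta(4, 97) gives 8.52%, below 8.6%. For 4/100, Beta(5, 96) gives 9.93%, above it. The stated cut-off of 3 is right.
- Power = P(X ≤ 3 | n = 100, p = 0.01) = 0.982, which agrees with the stated figure of over 90%.
- Type I error = P(X ≤ 3 | n = 100, p = 0.086) = 0.0235, within 0.025.
- Enrollment = 100 / (1 − 0.09) = 109.9, rounded up to 110.
- If all 110 are evaluable the limits are 7.76% (3 events) and 9.05% (4 events), so the cut-off is still 3.

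**How often one disagreement could matter.** A single disagreement reverses the verdict only if one source counts 3 and the other 4. The ceiling is P(X = 3) + P(X = 4) = P(X ≤ 4) − P(X ≤ 2), with n = 100:

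| True rate | P(X ≤ 4) | P(X ≤ 2) | Ceiling | P(X ≤ 3) |
|---|---|---|---|---|
| 1.0% (planned) | 0.9966 | 0.9206 | 7.6% | 98.2% |
| 2% (assumed) | 0.9492 | 0.6767 | 27.2% | 85.9% |
| 4.6% (meta-analysis upper bound) | 0.5106 | 0.1562 | 35.4% | 32.0% |

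Each ceiling must still be multiplied by the chance that the Monitor reviews recurrence at all and the chance that the two then differ on a pivotal case. The protocol gives neither. At 4.6% the study would usually miss its goal whoever decides.

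**The two rules side by side.**

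1. The sentence in Section 5.2.1 applies when imaging is done and is followed at once by the remark about a non-study imaging assessor. Read in place, it settles investigator against radiologist. It also governs the decision to report, which comes before any adjudication.
2. Section 13.1 governs what is analysed after adjudication. The two rules can operate in sequence: the investigator reports, the Monitor adjudicates if the event is on the list, and the Monitor's view prevails in analysis.
3. If recurrence is on the list, Section 13.1 names the determination to analyse. If it is not, the only determination is the investigator's. A disagreement rule therefore exists; only its scope is unstated.
4. The responsibilities table in Section 12.4.1 names relatedness, seriousness and diagnosis as what is classified. The surgical site occurrence endpoints in Section 5.2.2 require relatedness, so the Monitor's review clearly bears on them. The recurrence endpoint has no relatedness condition, so only a disagreement on diagnosis could change its count.
5. Section 16.2 requires form data to agree with source, discrepancies to be explained in writing, and programmed and manual checks with queries. A lasting mismatch between two forms, after the investigator has accepted the Monitor's view, is possible but speculative.
6. On outside records: Section 10.10 brings those recurrence and reoperation details into the study, Section 10.9 has suspected recurrences return for clinical assessment, Section 10.14.6 uses all data through exit, and Section 14.5 bases recurrence endpoints on a previous recurrence or evaluable data. Section 14.5 sits under the secondary objectives, but a sensible analyst would apply the same rule to the primary count.

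**The case for a change.** The strongest opposing argument concerns timing. Section 14 requires the analysis plan to be final only before the first data freeze or lock, while Section 12.4.1 has a sponsor representative review adverse events as they arrive. The sponsor could know of individual recurrences before anyone writes down whether the Monitor rules on them. Section 6 presents the Monitor as a measure against bias, and Section 14.10 relies on Section 6, so a reader would like to know whether that safeguard reaches the only hypothesis test. Appendix I does name recurrence as a foreseeable adverse event, so its inclusion is not far-fetched.

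What stands is that the list of adjudicated events is not in the readable text, and that it is better settled early than late. The rest does not carry. Appendix I is a risk list and does not set the Monitor's remit. Nothing shows that the Monitor adjudicates recurrence, either source would support a sound analysis, and no direction of bias follows from choosing one over the other. Unresolved disagreements must be reported with both determinations, so a reader could see whether the verdict depended on one. The synopsis sentence on which events the Monitor reviews is also broken in the text at hand, so its silence cannot be pressed far.

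**Conclusion.** No change to the protocol follows. Sections 6 and 13.1 leave the scope of adjudication unlisted, which is an ambiguity and not a demonstrated contradiction with Section 5.2.1. Each reading leads to a definite source for the primary count, and a list of adjudicated events, with the form that feeds an endpoint, is ordinary content for the analysis plan or an adjudication document, which may exist but is not shown here.

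The practical exposure is bounded. At the planned 1.0% rate, at most 7.6% of trials would have a count at which one disagreement could matter, before allowing for whether the Monitor reviews recurrence and how often the two would differ. The ceiling rises to 27.2% at an assumed 2% and 35.4% at 4.6%. These figures assume 100 evaluable subjects and independent events with a common rate. The conclusion also rests on reading the imaging sentence in Section 5.2.1 in its context and on the scope being recorded before the data freeze that Section 14 already sets.

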5.2.2 Secondary Endpoints

The secondary endpoints will include:

- Incidence of Surgical Site Occurrence (SSO) which are the following Adverse Events (AEs) related to the study device, mesh, and / or study procedure and defined as Seroma, Hematoma, Surgical Site Infection (SSI), bleeding at tack implantation site following the MaxTack[™] Motorized Fixation Device used for fixation in minimally invasive ventral hernia repair procedures at the following timepoints:
 - by Discharge
 - o within 1 month
 - within 3 months
 - within 12 months
- Incidence of SSO requiring Procedural Intervention (SSOPI), which are the following AEs related to the study device, mesh, and/or study procedure and defined as Seroma, Hematoma, Surgical Site Infection, bleeding at tack implantation site following the MaxTack[™] Motorized Fixation Device used for fixation in minimally invasive ventral hernia repair procedures at the following timepoints:
 - by Discharge
 - o within 1 month
 - o within 3 months
 - o within 12 months
- Incidence of hernia recurrence following the MaxTack[™] Motorized Fixation Device used for fixation in minimally invasive ventral hernia repair procedures. The evaluation of hernia recurrence will be performed via a Valsalva maneuver during a physical examination and confirmed per site standard of care medical imaging, if necessary, at the following timepoints:
 - \circ within 1 month
 - o within 12 months
- Incidence of hernia recurrences resulting in reoperation, defined as an operative procedure performed with the specific goal of repairing the recurrent hernia, at the following timepoints:

- o within 1 month
- \circ within 3 months
- within 12 months
- Incidence of MaxTack[™] Motorized Fixation Device deficiencies (e.g., insufficient tack penetration, loose tacks, tack(s) migration, tacker issue battery etc.) on day of the index procedure.
- Operative time for mesh fixation, defined as the time elapsed from the initiation of the mesh fixation process with MaxTack[™] to its completion
 - Surgeon satisfaction as assessed by Surgeon Satisfaction Questionnaire postoperatively.
 - Length of hospital stay after minimally invasive ventral hernia repair procedure where the MaxTack[™] Motorized Fixation Device was used for fixation.
- Change in subject-reported pain at the hernia site evaluated with Numeric Rating Scale (NRS) score from 0 to 10 at screening and compared to the following timepoints:
 - o at Month 1
 - o at Month 3
 - o at Month 12
 - Change in subject Quality of life (QoL), as measured through the administration of the Hernia Quality of Life Survey (HerQLes) questionnaire, evaluated at screening and compared to the following timepoints:
 - o at Month 1
 - o at Month 3
 - o at Month 12

6. Study Design

This prospective, post-market, multicenter, nonrandomized, single-arm, interventional clinical study will evaluate the performance and safety of the MaxTack[™] Motorized Fixation Device when used for fixation in minimally invasive ventral hernia repair procedures.

The study is expected to be conducted at approximately 10 study sites located in the United States (US). However, additional sites in other regions may be added as needed to meet study objectives. Approximately 110 subjects will be enrolled in the study using the MaxTack[™] Motorized Fixation Device. Enrolled subjects will be subjects who have signed an informed consent form, who meet all eligibility criteria and at least one MaxTack[™] tack is utilized for fixation. Study subjects will be evaluated at Screening (-60-0 days preoperative), Operative, Discharge, Month 1 (30-51 days postoperative), Month 3 (90-120 days postoperative), and Month 12 (365-410 days postoperative) visits.

Measures to control bias:

Enrollment parameters are included in the study to avoid introduction of bias to the study results due to disproportionate enrollment. Enrollment shall not exceed 25 subjects per site (this is 25% of the minimum

AFFIX (MaxTa Clinical Invest				
MDT23014	Revision	3.0	Page 24 of 97	Medtronic

number of evaluable subjects needed [100]). Enrollment will be competitive across study sites. The perstudy site enrollment cap may be increased upon sponsor approval. At any time, the study sponsor may place an enrollment hold on individual sites for reasons relating to data quality, overall performance, concerns with Principal Investigator (PI) oversight, or other reasons not specified within the Clinical Investigative Plan (CIP).

All investigators will be required to provide financial disclosure (FD). Physicians will not be able to participate if they have any significant conflict of interest that cannot be mitigated in this study.

Physicians performing procedures will be qualified surgeons experienced with hernia repair procedures.

A Medical Monitor (MM) will be utilized to conduct an independent review and adjudication of specified adverse events. The assessments from the MM will be used in the study endpoint analyses where applicable.

The expected total study duration from the first subject enrollment to the last subject visit is approximately 25 months, representing approximately 13 months of enrollment and 12 months (+ 45 days) of subject follow-up. Assessments will occur at Screening, Operative, Discharge, Month 1, Month 3, and Month 12. The expected duration of each subject's participation in the study from Screening visit to the Month 12 is up to 15.5 months (screening visit could occur 60 days prior to the Operative day, and with the Month 12 follow-up having an upper window of 45 days). Study subjects will be followed until the final study visit or official study closure, defined as when Medtronic requirements have been satisfied per the CIP and/or by a decision by Medtronic, Institutional Review Board (IRB), or Ethics Committee (EC), or Regulatory Authority (RA), whichever occurs first.

